1 PROTOCOL SUMMARY

1.1 SYNOPSIS

Title:

The effect of inflammation and damage to lymph node structures on durable protective immunity following yellow fever vaccination

Study Description:

Our hypothesis is that infections other than HIV can cause lymph node (LN) inflammation and collagen damage to the fibroblastic reticular cell network (FRCn), which will lead to CD4 T cell depletion and impaired vaccine responses. This protocol will study yellow fever vaccine (YFV) in two cohorts of people, one from Uganda and the other from Minnesota where we collect lymphoid tissues (LT) and peripheral blood monocytes (PBMCs) before and after vaccination using a new technique to catalog infectious burden of the individual, determine the relationship between IA, Infections, and immune response.

Objectives:

Primary Objective: To determine the relationship between endemic infections, immune activation (IA), T cell zone (TZ) fibrosis with loss of the fibroblastic reticular cell network (FRCn), CD4 and CD8 T cell subsets and the magnitude and durability of neutralizing antibody response to YFV in a cohort shown to have elevated IA, a damaged FRCn, and pan T cell depletion and a cohort that does not.

Endpoints:**Primary Endpoints:**

[figure not shown]
- 1) Peak titer of neutralizing antibody to yellow fever vaccination

Secondary Endpoints:

1. Measures of T cell zone fibrosis (collagen and desmin) in lymphatic tissue
2. Measures of past and present infection (pathseq, molecular analyses of helminth infection, serum antibody studies) in lymphatic tissue
3. Measures of immune activation (Ki67+ and CD69 + cells) in lymphatic tissue
4. Measures of systemic and lymphatic inflammation (plasma cytokines, frequency of TGF β + and TNF+ cells in lymphoid tissues) in lymphatic tissue
5. Histologic analyses of lymphoid tissues for T follicular helper cells, changes in B cell populations, measures of BAFF+ cells, changes to B cell follicles.
6. Size and change to the frequency of yellow fever antigen specific CD4+ T cell population in lymphatic tissues.
7. Changes in CD8 T cell number and function in lymphatic tissues measured with transcriptomic analyses and standard functional assays (stimulation assays).

Study Population:	This study will include two cohorts of healthy adults in Kampala, Uganda and in Minnesota, USA. The cohort in Uganda will be 30 adults (15 men and 15 women) and the cohort in Minnesota will be 16 adults (8 men and 8 women).
Phase:	N/A

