4 STUDY DESIGN

4.1 OVERALL DESIGN

The primary aim of this study is to determine the difference between antibody titers in the two study groups and study the relationship between endemic infections, IA, the FRCn, and CD4 and CD8 T cell subsets and the magnitude and durability of neutralizing antibody response to YFV in a cohort shown to have elevated IA, a damaged FRCn, and pan T cell depletion and a cohort that does not. This is a single arm, open-label, two cohort study of healthy adults in Kampala, Uganda and in Minnesota, USA. The cohort in Uganda will be 30 adults (15 men and 15 women) and the cohort in Minnesota will be 16 adults (8 men and 8 women). Everyone will be screened to ensure there are no contraindications to receiving YFV (e.g., immunosuppression) or the planned procedures. The inclusion and exclusion criteria are discussed in detail in the protocol that is included in the appendix. Participants will have an inguinal LN biopsy and leukapheresis prior to YFV and another LN biopsy 3 weeks after the vaccine administration. The vaccine will be given in the contralateral thigh from the first LN biopsy so that the second biopsy will be from a draining LN. PBMC and plasma will be collected at regular intervals over the 18-month follow-up period. Leukapheresis will be done again at the month 6 visit.

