8.2 SAFETY AND OTHER ASSESSMENTS

Screening Procedures (Day -42 to 1)

Participants will be consented by the investigator or qualified study staff before any procedures take place.

The following screening blood tests will be obtained:

- CBCD
- Chemistry Panel (including Albumin, ALT, AST, Alk. Phosphate, Bilirubin (total), Calcium, Chloride, CO₂, Creatinine, Glucose, Potassium, Protein (total), Sodium, Urea Nitrogen)
- T Cell Panel
- PT/PTT
- HIV antibody
- Yellow Fever Neutralizing Antibody
- PBMC/Plasma storage (to screen for yellow fever)

We will obtain a detailed medical history to ascertain that potential subjects have not had yellow fever, been vaccinated for yellow fever, and have no history of thymus disease. Females of childbearing

potential will have a serum or urine pregnancy test. During the COVID-19 pandemic, participants will be screened for COVID-19 symptoms before coming in for their visit.

Baseline Procedures (Day -35 to 1)

Medical history and concurrent medications ascertained. Physical examination and vital signs, including blood pressure, pulse and weight will be conducted. There will also be an AE assessment. Leukapheresis will be performed. Before Leukapheresis, females of childbearing potential will have a serum or urine pregnancy test. If a participant is not eligible for leukapheresis based on the apheresis consultation appointment or is unable to tolerate leukapheresis, a large volume blood draw (60 cc) will be done instead. Participants will undergo a lymph node biopsy tissue will be stored. Participants will have stool and urine collected for a helminth check. Stool will be collected for microbiome study.

Blood will be collected for:

- T cell panel
- Luminex
- PBMC/plasma storage

During the COVID-19 pandemic, participants will be screened for COVID-19 symptoms before coming in for their visits.

Day 1

Yellow fever vaccine will be administered. During the COVID-19 pandemic, participants will follow the travel clinics' procedures for screening of COVID-19 symptoms before coming in for their visit.

Days 3 through 14

Participants will return every 2 to 3 days (see SOEs, Sections 1.2 and 1.3) for blood collection for:

- PBMC/plasma storage
- Yellow fever neutralizing antibody

Stool will be collected on Day 10 for microbiome study.

On Days 7 and 14, females of childbearing potential will have a serum or urine pregnancy test.

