During the COVID-19 pandemic, participants will be screened for COVID-19 symptoms before coming in for their visits. There will also be AE assessments.

Day 17

At Day 17, participants will have a research blood draw of 60 cc. Blood will be collected for yellow fever neutralizing antibody. There will also be an AE assessment. During the COVID-19 pandemic, participants will be screened for COVID-19 symptoms before coming in for their visit.

Week 3

At Week 3, participants will undergo a lymph node biopsy will be stored. Blood will be collected for:

- T cell panel
- Luminex
- PBMC/plasma storage

Females of childbearing potential will have a serum or urine pregnancy test. There will also be an AE assessment. During the COVID-19 pandemic, participants will be screened for COVID-19 symptoms before coming in for their visit.

Weeks 4 through 10

Participants will return every 2 weeks (see SOEs, Sections 1.2 and 1.3) for blood draws for:

- PBMC/plasma storage
- Yellow fever neutralizing antibody (week 8 only)

At Week 4, females of childbearing potential will have a serum or urine pregnancy test. Stool will be collected for microbiome study.

There will also be an AE assessment. During the COVID-19 pandemic, participants will be screened for COVID-19 symptoms before coming in for their visit.

Week 12

Blood will be collected for:

- HIV antibody
- PBMC/plasma storage
- Luminex

Stool and urine will be collected to check for helminths. There will also be an AE assessment. During the COVID-19 pandemic, participants will be screened for COVID-19 symptoms before coming in for their visit.

Months 6 through 15

Participants will return quarterly starting Month 6 through Month 18.

Months 6, 9, 12 and 15 participants will have blood collected for PBMC/plasma storage.

Month 6 will have stool will be collected for microbiome study. During the month 6 timepoint, leukapheresis will be performed. Before leukapheresis, females of childbearing potential will have a serum or urine pregnancy test. If a participant is not eligible or unable to tolerate leukapheresis, a large volume blood draw (60 cc) will be done.

At the month 12 visit, participants will have stool and urine collected for helminth check. Stool will be collected for microbiome study, and blood will be collected for:

- HIV antibody
- Luminex
- PBMC/plasma storage

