Null hypothesis: There is no association between CD4, CD8 functional variables and CD4 subsets and peak specific IgM, IgG1, IgG2, IgG3 and IgG4 responses or rate of change. Alternative hypothesis: There is an association between CD4, CD8 functional variables and CD4 subsets and peak specific IgM, IgG1, IgG2, IgG3 and IgG4 responses or rate of change.

Null hypothesis: There is no change in immune activation or inflammation measures or CD4 and CD8 cells after immunization. Alternative hypothesis: There is a change in immune activation or inflammation measures or CD4 and CD8 cells after immunization.

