The association between change in measures of CD8 function (IFN γ , TNF α , and IL-2) after vaccination and measures of LN architecture will be examined by fitting mixed effects linear models using area with collagen staining, area with desmin staining, and measurement time and gender as predictors.

The association between immune function after vaccination and measures of inflammation and activation will be assessed using separate lasso regression for each measure of immune function (antigen specific CD4, CD8 function measures, and CD4 and CD8 subpopulations). Inflammation and activation measures which have non-zero coefficients in the model will be considered predictive of immune function.

We will examine the impact of measures of immune function on YFV response using separate mixed effects linear models with gender, measurement time and measures of immune function (antigen specific CD4, CD8 functional variables, or CD4 and CD8 subpopulations) as predictors. Similar models will be fit for YF specific IgM, IgG1, IgG2, IgG3 and IgG4 responses.

The impact of vaccination on measures of inflammation and activation be assessed using mixed effects repeated measures model with gender, measurement time, and vaccination status as predictors. To assess the impact of vaccination on CD4 and CD8 cells in LT similar models will be fit, but only gender and vaccination status (measurement taken before or after vaccination) will be used as predictors.

Missing data will not be imputed and a significance level of 0.01 will be used for secondary analyses due to the large number of hypotheses to be tested. The results from all of these investigations will be reported so that the reader can assess the effect of multiple hypothesis testing.

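### For lymph node inflammation and activation, the before/after model in 9.4.3 enters measurement time and vaccination status together, and two biopsies in one vaccinated arm cannot support both; for cytokines the two separate only through an assumed straight line in time

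*Combined protocol and SAP*

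**What the plan says.** Section 9.1 lists as a secondary null hypothesis: "There is no change in immune activation or inflammation measures or CD4 and CD8 cells after immunization". For the inflammation and activation part, 9.4.3 gives a "mixed effects repeated measures model with gender, measurement time, and vaccination status as predictors". The next sentence covers CD4 and CD8 cells in lymphoid tissue with a similar model, except that "only gender and vaccination status (measurement taken before or after vaccination) will be used as predictors". The form of measurement time (visit or days) is not stated for this model.

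The outcomes come from two sampling schedules.

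- **Tissue.** The Synopsis lists "Measures of immune activation (Ki67+ and CD69 + cells) in lymphatic tissue" and, under inflammation, the frequency of TGFβ+ and TNF+ cells in lymphoid tissue. Section 4.1 says "Participants will have an inguinal LN biopsy and leukapheresis prior to YFV and another LN biopsy 3 weeks after the vaccine administration". Section 8.2 puts the first biopsy in the block headed "Baseline Procedures (Day -35 to 1" and gives the second as "At Week 3, participants will undergo a lymph node biopsy will be stored".
- **Plasma cytokines.** Section 8.2 lists Luminex once before vaccination, then at Week 3, Week 12, Month 12 and Month 18.

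The schedule table in 1.3, as extracted, places some marks in neighbouring columns. It still shows one pre-vaccination mark for each. Section 4.1 adds: "This is a single arm, open-label, two cohort study of healthy adults".

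**The concern.** A model can estimate a vaccination effect and a time effect together only if some records share a time but differ in vaccination status, or if several pre-vaccination records reveal the time course by themselves. This study has neither. No cohort is followed unvaccinated, and each outcome has a single pre-vaccination sample. An enrollee who is never vaccinated would add only pre-vaccination records, which does not help.

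This is the only model that 9.4.3 gives for the inflammation and activation part of that hypothesis. The pilot in section 2.2 reported a rise in Ki67+ cells after vaccination (p=0.002), so a tissue change is a realistic finding. What the planned model reports about it would depend on a coding choice that the plan leaves open.

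**Working it through.** The plan gives no figure for this model, so there is none to reproduce. The check covers the design matrix and the precision that follows from it.

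**Inputs from the documents:** 46 participants (30 + 16, section 9.2); biopsies at baseline (up to 35 days before vaccination) and Week 3 (±1 day); Luminex at baseline and about days 21, 84, 365 and 548; secondary alpha 0.01, two-sided; subject random effects (9.4.1). **Assumed:** both biopsies available for everyone, total variance 1, within-person correlation ρ of 0.3 to 0.7, and for power a true change of 0.6 SD. Days are counted from vaccination.

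**1. Time coded by visit (needs no assumption).**
- Tissue columns are intercept, gender, Week 3 indicator and after-vaccination indicator. The last two are identical: 4 columns, rank 3.
- Luminex columns are intercept, gender, four visit indicators and status. Status is the sum of the four indicators: 7 columns, rank 6.

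**2. Tissue, actual days.** Without time, the standard error (SE) of the before/after term is √(2(1−ρ)/46), which is √(1/46) = 0.147 at ρ = 0.5. If the day is added and only within-person differences are used, the SE grows by √(1 + m²/v), where m and v are the mean and variance of the gap between biopsies.
- Baseline spread evenly over days −35 to 0: m = 21 + 17.5 = 38.5 and v = 35²/12 + 2²/12 = 102.4. The factor is √(1 + 1482/102.4) = 3.9.
- Baseline within days −7 to 0: m = 24.5 and v = 7²/12 + 2²/12 = 4.42. The factor is √(1 + 600/4.42) = 11.7.

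The random-intercept model also uses differences between people in biopsy date, which lowers these factors somewhat. Generalised least squares gives the following; ranges in the second and third columns run from dates in whole days to continuous dates.

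| Baseline biopsies within | SE with day, ρ = 0.5 | Ratio, ρ = 0.5 | Ratio, ρ = 0.3 to 0.7 | Power, 0.6 SD, ρ = 0.5 |
|---|---|---|---|---|
| days −35 to 0 | 0.50 to 0.51 | 3.4 to 3.5 | 3.2 to 3.7 | 8% |
| days −7 to 0 | 1.31 to 1.51 | 8.9 to 10.3 | 8.3 to 11.0 | about 2% |
| days −21 to −14 | 2.05 to 2.39 | 13.9 to 16.2 | 13.0 to 17.1 | about 1% |

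Without the time term, power is 93% (0.6/0.147 = 4.07, against a critical value of 2.58).

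**3. Cytokines, time linear in days.** The matrix now has full rank, 4 of 4. The single baseline sample is fitted exactly, so the slope comes from the four later visits alone. The status coefficient is the post-vaccination line carried back to the baseline day, minus the baseline value. The later visits average day 254.5, with sum of squared deviations 181,945.
- Rise of 1 SD at Week 3 only: slope = (21 − 254.5)/181,945 = −0.001283. Coefficient = 0.25 + 0.001283 × 254.5 = 0.58 with baseline at day 0, or 0.25 + 0.001283 × 289.5 = 0.62 with baseline at day −35.
- Change of 1 SD at Month 18 only: slope = (548 − 254.5)/181,945 = 0.001613. Coefficient = 0.25 − 0.001613 × 254.5 = −0.16, or −0.22 with baseline at day −35.
- Sustained change of 1 SD at all four visits: slope 0, coefficient 1.0.
- With log(1 + day) in place of day, the Week 3 rise gives 1.66. The answer depends on an unstated form of time.

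**The case against.** **Visit-coded tissue loses no information.** Removing either duplicate column leaves Week 3 minus baseline at full precision, and the redundancy shows at the first fit. This stands. In that case the fault is a model that cannot be run as written, and no power is lost.

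**The power loss is conditional.** It arises only if actual biopsy days are entered and kept despite the collinearity, and the effect size, correlations and date spreads are all assumed. This stands too. A reader might infer that a real tissue change would probably be missed; the documents do not support that, because they do not say days will be used. Still, 9.4.3 uses measurement time to estimate a decay rate elsewhere, which suggests continuous time is a live option. The permutation p-values in 9.4.1 change the reference distribution and do not remove the collinearity, so the ratios stand; the power figures are normal approximations.

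**The cytokine model is workable.** With linear days it is full rank, with a variance inflation factor of 1.28, and it recovers a sustained change exactly. For a Week 3 rise of 1 SD at ρ = 0.5, it has 96% to 98% power, against 33% for status without time. So simply deleting time from the cytokine model would be worse. This also stands. What remains is that the size of the effect rests on a straight line.

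**A false cytokine effect is unlikely.** A reader might infer that late drift would be reported as a vaccination effect. The Month 18 profile gives −0.16 to −0.22 with an SE of about 0.13, significant at 0.01 in roughly 9% to 16% of trials at ρ = 0.5 (6% to 30% across ρ of 0.3 to 0.7). That exceeds 1%, but non-significance is the likelier result even for so extreme a profile.

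**Conclusion.** The concern holds, in two parts of unequal strength.

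For lymph node inflammation and activation, the model is wrong as written. It gives no separate vaccination estimate with visit-coded time, which rests on the schedule alone. With day-coded time the estimate has an SE about 3.2 to 3.7 times larger (whole baseline window) or roughly 8 to 17 times larger (7-day windows between day −21 and day 0), under the stated assumptions. The adjacent CD4/CD8 sentence already handles the same two biopsies correctly.

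For plasma cytokines the point is milder. The terms are aliased only if time is coded by visit. A reader might infer that time and vaccination can never be separated here, but with continuous time and four later samples both can be estimated. The price is a straight-line assumption over 18 months that the hypothesis does not need and that shrinks a Week 3 rise to about 0.6 of its size.

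This affects one secondary hypothesis. The primary Mann-Whitney comparison is untouched. The plan should be changed, since the change is small.

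**What to change.** Rewrite two sentences of 9.4.3.

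- **Tissue (Ki67+, CD69+, TGFβ+, TNF+ cells):** extend the model already given for CD4 and CD8 cells in lymphoid tissue, with gender and before/after status, a subject random effect and no measurement time.
- **Plasma cytokines:** fit gender and visit as a five-level factor, and drop the separate vaccination-status term. Name Week 3 minus baseline as the vaccination contrast, and report Week 12, Month 12 and Month 18 minus baseline as follow-up.

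Describe both as change after vaccination, as 9.1 does. Neither model separates vaccination from anything else that changes over the same period, because there is no unvaccinated comparator.

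The cost is text only: no new draw, biopsy, assay or visit. The small downside is that a sustained cytokine change is no longer pooled over visits in one coefficient. At ρ = 0.5 the Week 3 contrast has an SE of 0.147, against 0.132 to 0.136 for the status term in the linear-time model.

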9.4.4 SAFETY ANALYSES

Any AEs will be reported annually in a study report that will document AEs and completeness of data. This report will include the total number of AEs for each cohort and the total number of participants in each cohort that experience an AE. AEs will be summarized in terms of severity and relatedness and the number of participants experiencing SAEs will also be reported for each cohort. A line listing will also be included in this report.

9.4.5 BASELINE DESCRIPTIVE STATISTICS

Demographic baseline characteristics will be compared between the MN and Ugandan populations using Mann-Whitney U tests (continuous outcomes) or Fisher's exact test (categorical outcomes).

9.4.6 PLANNED INTERIM ANALYSES

N/A- There is no planned interim analysis.

9.4.7 SUB-GROUP ANALYSES

In addition to including gender, we will assess how additional clinical factors (such as age and other demographic variables) influence immune response to vaccination by including relevant clinical factors in to our models.

9.4.8 TABULATION OF INDIVIDUAL PARTICIPANT DATA

Individual participant data will not be listed by measure and time point.

9.4.9 EXPLORATORY ANALYSES

The association between change in the CD4 and CD8 T cell populations after vaccination and measures of LN architecture will be examined by fitting mixed effects linear models estimating T cells populations using area with collagen staining, area with desmin staining, and measurement time and gender as predictors.

10 SUPPORTING DOCUMENTATION AND OPERATIONAL CONSIDERATIONS

10.1 REGULATORY, ETHICAL, AND STUDY OVERSIGHT CONSIDERATIONS

10.1.1 INFORMED CONSENT PROCESS

10.1.1.1 CONSENT/ASSENT AND OTHER INFORMATIONAL DOCUMENTS PROVIDED TO PARTICIPANTS

A signed consent form will be obtained from the participant. The consent form will describe the purpose of the study, the procedures to be followed, and the risks and benefits of participation. A copy of the consent form will be given to the participant, and this fact will be documented in the participant's record.

Research staff will ensure that candidates understand all elements of the consent form by addressing questions posed during the consent procedure and by asking for verbal confirmation that the candidate has no additional questions and verbally understands the purpose of the study, study intervention, basic procedures, risks, and that participation is voluntary. Participants will be given as much time as they need to read and understand the consent form.

10.1.1.2 CONSENT PROCEDURES AND DOCUMENTATION

Informed consent is a process that is initiated prior to the individual's agreeing to participate in the study and continues throughout the individual's study participation. Consent forms will be Institutional Review Board (IRB)-approved and the participant will be asked to read and review the document. The investigator will explain the research study to the participant and answer any questions that may arise. A verbal explanation will be provided in terms suited to the participant's comprehension of the purposes, procedures, and potential risks of the study and of their rights as research participants. Participants will have the opportunity to carefully review the written consent form and ask questions prior to signing. The participants should have the opportunity to discuss the study with their family or surrogates or think about it prior to agreeing to participate. The participant will sign the informed consent document prior to any procedures being done specifically for the study. Participants must be informed that participation is voluntary and that they may withdraw from the study at any time, without prejudice. A copy of the informed consent document will be given to the participants for their records. The informed consent process will be conducted and documented in the source document (including the date), and the form signed, before the participant undergoes any study-specific procedures. The rights and welfare of the participants will be protected by emphasizing to them that the quality of their medical care will not be adversely affected if they decline to participate in this study.

